8.2.2. Vital Signs

- Oral temperature, pulse rate, respiratory rate, and systolic and diastolic blood pressure (mm Hg) will be assessed.
- Routine blood pressure and pulse measurements will be assessed with a completely automated device. Manual techniques should be used if repeat measurements are necessary due to abnormal results.
- Blood pressure and pulse measurements should be preceded by at least 5 minutes of rest for the participant in a quiet setting without distractions (eg, television, cell phones). Ideally, the same arm for each participant should be used for measurements.

8.2.3. Vital signs will be measured in a semi-supine position after 5 minutes rest. Electrocardiograms

• Participants will be resting in the supine position for at least 15 minutes prior to and 5 minutes after each nominal time point for ECG extraction. Triplicate 12-lead ECG will be conducted as outlined in the SoA (see Table 1) to obtain heart rate, PR, QRS, QT, and QTc intervals. Heart rate and interval data will be recorded in the eCRF. QT corrected for heart rate using Fridericia's formula should be recorded as the QTc reading (unless unavailable and then QTcB may be recorded). Refer to Section 7 for QTc withdrawal criteria and any additional QTc readings that may be necessary.

8.2.4. Clinical Safety Laboratory Assessments

- See Section 10.2 for the list of clinical laboratory tests to be performed and the SoA (Table 1) for the timing and frequency.
- The Investigator must review the laboratory report, document this review, and record any clinically relevant changes occurring during the study in the AE section of the CRF. At the Investigator's discretion, all abnormal values may be repeated to confirm results. The laboratory reports must be filed with the source documents.
- All laboratory tests with values considered clinically significantly abnormal during participation in the study after the last dose of the study intervention should be repeated until the values return to normal or baseline or are no longer considered clinically significant by the Investigator or Medical Monitor.
 - If such values do not return to normal/baseline within a period of time judged reasonable by the Investigator, the etiology should be identified, and Alexion notified.
 - All protocol-required laboratory assessments, as defined in Section 10.2, must be conducted in accordance with the laboratory manual and the SoA (Table 1).
 - All laboratory values from nonprotocol specified laboratory assessments also must be recorded in the CRF.

8.2.5. Suicidal Ideation and Behavior Risk Monitoring

For bupropion, as stated in the WELLBUTRIN SR USPI (WELLBUTRIN SR), there is "Increased risk of suicidal thinking and behavior in children, adolescents and young adults taking antidepressants. All patients should be monitored for worsening and emergence of suicidal thoughts and behaviors". This will be monitored throughout the study as listed in the SOA (Table 1) under "AE monitoring and concomitant therapies review".

8.2.6. Pregnancy

- Pregnancy data from female participants and female spouses/partners of male participants will be collected from the first dose of the study intervention through 90 days post the last dose and at the time points specified in the SoA. Any female participant who becomes pregnant while participating in the study will be discontinued from the study intervention. If a pregnancy is reported, the Investigator must immediately inform Alexion within 24 hours of awareness of the pregnancy and follow the procedures outlined in Section 10.4.
- For all Alexion products, both in development or post-approval, exposure during pregnancy must be recorded and the pregnancy followed until the outcome of the pregnancy is known (ie, spontaneous miscarriage, elective termination, normal birth, or congenital abnormality), even if the participant discontinues study intervention or withdraws from the study. The corresponding infant must be followed for 3 months postpartum.
- Pregnancy is not considered an AE (Section 10.4) unless there is a suspicion that the study intervention may have interfered with the effectiveness of a contraceptive medication. However, complications of pregnancy and abnormal outcomes of pregnancy are AEs and may meet the criteria for a SAE (eg, ectopic pregnancy, spontaneous abortion, intrauterine fetal demise, neonatal death, or congenital anomaly) (Section 8.3). Elective abortions without complications should not be reported as AEs.

8.3. Adverse Events and Serious Adverse Events

The definitions of AEs and SAEs can be found in Section 10.3.

Adverse events will be reported to the Investigator or qualified designee by the participant (or, when appropriate, by a caregiver, surrogate, or the participant's legally authorized representative).

The Investigator and any qualified designees are responsible for detecting, documenting, and recording events that meet the definition of an AE or SAE and remain responsible for following up AEs that are serious, considered related to the study intervention or study procedures, or that caused the participant to discontinue the study (see Section 7).

Procedures for recording, evaluating, follow-up, and reporting AEs and SAEs are outlined in Section 10.3.

8.3.1. Time Period and Frequency for Collecting Adverse Event and Serious Adverse Event Information

All AEs will be collected from the signing of the ICF until the EOS or ET Visit.

All SAEs will be recorded and reported to Alexion or the designee immediately and under no circumstance should this exceed 24 hours, as indicated in Section 10.3. The Investigator will submit any updated SAE data to Alexion within 24 hours of it being available.

Investigators are not obligated to actively seek AEs or SAEs after conclusion of the study participation. However, if the Investigator learns of any SAE, including a death, at any time after a participant has exited the study, and he/she considers the event to be reasonably related to the study intervention, the Investigator must promptly notify Alexion.

8.3.2. Method of Detecting AEs and SAEs

The method of recording, evaluating, and assessing causality of AEs and SAEs and the procedures for completing and transmitting SAE reports are provided in Section 10.3.

Care will be taken not to introduce bias when detecting AEs and/or SAEs. Open-ended and non-leading verbal questioning of the participant is the preferred method to inquire about AE occurrences.

8.3.3. Follow-up of AEs and SAEs

After the initial AE/SAE report, the Investigator is required to proactively follow-up with each participant at subsequent visits/contacts. All SAEs will be followed until resolution, stabilization, the event is otherwise explained, or the participant is lost to follow-up (as defined in Section 7.3). Further information on follow-up procedures is provided in Section 10.3.

8.3.4. Regulatory Reporting Requirements for SAEs

- Prompt notification by the Investigator to Alexion of an SAE is essential so that legal obligations and ethical responsibilities towards the safety of participants and the safety of a study intervention under clinical investigation are met.
- Alexion has a legal responsibility to notify both the local regulatory authority and other regulatory agencies about the safety of a study intervention under clinical investigation. Alexion will comply with country-specific regulatory requirements relating to safety reporting to the regulatory authority, Institutional Review Boards (IRBs)/Independent Ethics Committees (IECs), and Investigators.
- Suspected unexpected serious adverse reactions (SUSARs) must be reported according to local regulatory requirements and Alexion policy and forwarded to Investigators as necessary.
- An Investigator who receives an Investigator Safety Report describing an SAE or
 other specific safety information (eg, summary or listing of SAEs) from Alexion will
 review and then file it along with the IB and will notify the IRB/IEC, if appropriate
 according to local requirements.

8.3.5. Adverse Events of Special Interest

There are no adverse events of special interest for this study.

8.3.6. Retained and Biobanked Sample

A single biobanked serum sample will be collected pre-dose to serve as a retained safety sample during the study. At the end of the study, pre-dose safety samples will be biobanked to support assay development and determination of normal Cu and Mo levels in healthy participants. Samples may be stored and used for up to 5 years following completion of the study.

8.4. Treatment of Overdose

For this study, any dose of ALXN1840 or bupropion greater than that specified in the protocol will be considered an overdose.

Alexion does not recommend specific treatment for an overdose.

Overdoses are medication errors that are not considered AEs unless there is an untoward medical occurrence resulting from the overdose.

In the event of an overdose or suspected overdose, the Investigator or treating physician should:

- Contact the Medical Monitor immediately.
- Closely monitor the participant for any AE/SAE.
- Obtain a plasma sample for PK analysis if requested by the Medical Monitor (determined on a case-by-case basis).
- Document the quantity of the excess dose as well as the duration of the overdose in the CRF.

Decisions regarding dose interruptions or modifications will be made by the Investigator in consultation with the Medical Monitor based on the clinical evaluation of the participant.

8.5. Pharmacokinetics

- Whole blood samples will be collected for the measurement of plasma concentrations of total Mo, bupropion and its metabolite hydroxybupropion as specified in the SoA (Table 1). Additional samples may be collected at additional time points during the study if warranted and agreed upon between the Investigator and Alexion. Collection of samples for PK evaluation should occur as close as possible to the scheduled time and actual time of collection should be documented on the eCRF. Samples collected within ± 10% of the scheduled time or 30 minutes, whichever is less, will not be considered a protocol deviation. In the event of a safety occurrence and after agreement between the Investigator and Medical Monitor, up to 3 additional PK sampling timepoints may be added.
- Instructions for the collection and handling of biological samples will be provided by Alexion. The actual date and time (24-hour clock time) of each sample will be recorded.

- Samples will be used to evaluate the effect of ALXN1840 on the PK of bupropion. Samples collected for analyses of plasma concentrations may also be used to evaluate safety or efficacy aspects related to concerns arising during or after the study.
- Excess/additional samples may be stored for up to 5 years and used for pharmacodynamic (PD) development and research to understand the pathways associated with the mechanism of action of ALXN1840; however, samples will not be used for genetic analyses (ie RNA or DNA analyses).

8.6. Pharmacodynamics

Plasma samples collected for PK may be used for analyzing the PD of ALXN1840 including, but not limited to plasma total Cu, ceruloplasmin (Cp), Cp-bound Cu (CpC), and potentially toxic Cu measured as labile-bound Cu (LBC) and PUF Cu and/or NCC/NCC_{corrected}.

8.7. Genetics

Blood samples for genetic testing of CYP2B6 polymorphism will be collected at clinical Check-in (Day -1). This study proposes to collect genetic polymorphism data to characterize potential impact of ALXN1840 on phenotypic CYP2B6 metabolism of bupropion and evaluate the potential effect of genetic polymorphism on the between-participant variability of bupropion PK. As this is an exploratory assessment, the study will not specifically select target participants with a certain proportion of CYP2B6 genotypes.

8.8. Biomarkers

Biomarkers are not evaluated in this study.

8.9. Immunogenicity

Not applicable.

8.10. Health Economics and Medical Resource Utilization

Health economic and medical resource utilization parameters are not evaluated in this study.

9. STATISTICAL CONSIDERATIONS

9.1. Statistical Hypotheses

The primary objective is to determine the effect of ALXN1840 on the PK of bupropion. There is no formal null hypothesis to be statistically tested and used to drive declaration of study success or failure.

To assure the study has enough participants, to estimate the inhibitory effect of ALXN1840 on the metabolism of bupropion with adequate precision, the sample size was determined using the conservative 90% confidence interval (CI) and 80% to 125% no-effect boundary approach described in the FDA Guidance "Clinical Drug Interaction Studies — Cytochrome P450 Enzyme- and Transporter Mediated Drug Interactions" (2020). This guidance notes the 80 to 125% boundaries represent a very conservative standard for drugs that have wide safety "margins" and "the totality of evidence should be taken into consideration when determining the clinical impact of the DDI on the substrate drug". Therefore, if the estimated inhibition effect of ALXN1840 on bupropion PK lies outside this no-effect boundary, this should not be interpreted as a failed study.

9.2. Sample Size Determination

A default of no-effect boundary (80% to 125%) approach will be employed to assess whether there is an inhibition effect on the metabolism of bupropion in the presence of ALXN1840. For a 2-period crossover study design, assuming the true ratio of the means (bupropion + ALXN1840 vs bupropion alone) on the PK parameters is 1 (C_{max} ; area under the plasma concentration versus time curve from zero to infinity [AUC $_{\infty}$]) and the bupropion intra-participant coefficient of variation (CV) is 0.30 (Dennison, 2018), a total sample size of 32 completed participants can achieve 90% power with two 1-sided tests, each with a type I error rate of 5% (two-sided type I error rate of 10%). The intra-participant CV is estimated using residual mean-square error (MSE) term in the ANOVA model. The CV is estimated as 100% × $\sqrt{}$ (exp (MSE) - 1) for the log-transformed PK parameters.

Assuming a 15% dropout rate, approximately 38 participants were planned to be enrolled and randomized in the original protocol. This protocol amendment is increasing the planned enrollment number because 17 of the 31 randomized participants (as of the date of this amendment) were anticipated to not have viable PK samples (pending further bioanalytical stability investigation) following a power outage at the CRU during study conduct. To reach the sample size of 32 completed participants necessary for sufficient study power as previously described, an additional 21 participants will be randomized to complete at least 18 of the 21 (assuming a similar 15% dropout rate for the additionally enrolled participants). Therefore, a total of approximately 52 participants will now be randomized in this study to still reach the aim of at least 32 completed participants.

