4.2. Sample Size

A default of no-effect boundary (80% to 125%) approach will be employed to assess whether there is an inhibition effect on the metabolism of bupropion in the presence of ALXN1840. For a 2-period crossover study design, assuming the true ratio of the means (bupropion + ALXN1840 vs bupropion alone) on the PK parameters is 1 (C_{max} ; AUC_{∞}) and the bupropion intra-participant coefficient of variation (CV) is 0.30 (Dennison, 2018), a total sample size of 32 participants can achieve 90% power with two 1-sided tests, each with a type I error rate of 5% (two-sided type I error rate of 10%). The intra-participant CV is estimated using residual mean-square error (MSE) term in the analysis of variance model. The CV is estimated as $100\% \times \sqrt{(\exp(MSE) - 1)}$ for the log-transformed PK parameters. Assuming a 15% dropout rate, approximately 38 participants will be enrolled.

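### With 32 completers the plan's own inputs give about 82% power for the two one-sided tests, not the stated 90%, and the amended size of 52 rests on the same figure.

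*Protocol*

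**What the plan says.** Protocol 9.2 gives the full set of planning inputs. The setting is "For a 2-period crossover study design", and the criterion is the default FDA one: "A default of no-effect boundary (80% to 125%) approach will be employed". The calculation proceeds "assuming the true ratio of the means (bupropion + ALXN1840 vs bupropion alone) on the PK parameters is 1", naming Cmax and AUC∞, and takes it that the bupropion "intra-participant coefficient of variation (CV) is 0.30". Each one-sided test is at 5%. The CV is tied to the residual mean square "for the log-transformed PK parameters", so the scale is explicit. The conclusion is that "a total sample size of 32 completed participants can achieve 90% power with two 1-sided tests".

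SAP 4.2 repeats the inputs and concludes that "a total sample size of 32 participants can achieve 90% power with two 1-sided tests".

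Amendment 1 carries the figure forward. After the power outage, 17 of 31 randomized participants were expected to have no viable PK samples. Protocol 9.2 then justifies 21 further randomizations with the words "To reach the sample size of 32 completed participants necessary for sufficient study power as previously described", and arrives at about 52 in total.

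Protocol 9.1 and SAP 4.1 add that no formal hypothesis decides success or failure, and that the size was chosen for adequate precision by way of the 90% CI and the 80% to 125% bounds.

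**The concern.** The no-effect conclusion requires the whole 90% CI to lie within 80% to 125%, so both one-sided tests must reject. At a true ratio of 1 the estimate can miss on either side with equal probability, and both kinds of miss count. A claim of 90% power should therefore refer to the joint event. For 32 completers at a CV of 0.30, 90% looked too high for the joint event and about right for one test alone.

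Three things are at stake:

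- Both governing documents would state a type II error of 10% when the design has nearly twice that.
- The amendment's case for randomizing 21 more volunteers would cite a power the design does not have.
- If the 90% CI crosses a bound, readers who believe the study had 90% power will be quicker to read the result as an interaction than the design warrants.

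**Working it through.** **Inputs** (Protocol 9.2, repeated in SAP 4.2): 2×2 crossover; true ratio 1; CV 0.30 on the log scale; bounds 0.80 to 1.25; 5% per one-sided test; N = 32. The only addition is an even 16/16 split of completers, which is the most favourable split.

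**Step 1, log-scale quantities.**

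- Within-participant SD: σ = √ln(1 + 0.30²) = √ln(1.09) = 0.2936
- Standard error of the treatment difference: SE = σ√(2/N) = 0.2936 × √(2/32) = 0.0734
- Degrees of freedom: N − 2 = 30, with t(0.95; 30) = 1.697
- Distance from the true value to each bound: ln 1.25 = −ln 0.80 = 0.2231, which is 0.2231/0.0734 = 3.04 standard errors

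**Step 2, try to reproduce 90%.** For one one-sided test, the noncentral t distribution with noncentrality 3.04 and 30 df gives power 0.908. N = 30 gives 0.890, so 32 is the smallest even N that reaches 90% on a single test. This is the only reading using the stated CV and the stated 5% level that comes close to the stated figure.

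**Step 3, power for both tests.** By symmetry at a ratio of 1, each test fails with probability 1 − 0.9076 = 0.0924. Both failing together is negligible here, so joint power is 1 − 2 × 0.0924 = 0.815. Exact integration over the chi distribution of the estimated SD gives 0.8152. Simulation with 400,000 runs gives 0.817.

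**Step 4, other readings at N = 32.**

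| Reading | Power |
|---|---|
| Exact, as stated | 81.5% |
| Variance treated as known (normal) | 83.7% |
| Paired analysis, 31 df | 81.6% |
| 0.30 taken directly as the log SD | 79.3% |
| Untransformed scale, bounds 0.80–1.25 | 77.8% |
| Untransformed scale, bounds ±20% | 66.3% |
| *Contradicts the text:* one test only | 90.8% |
| *Contradicts the text:* 10% per test | 91.4% |
| *Contradicts the text:* CV 0.27 | 90.0% |

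**Step 5, N needed.** Exact power for both tests at CV 0.30 and ratio 1:

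| Completers | 30 | 32 | 34 | 36 | 38 | 39 | 40 |
|---|---|---|---|---|---|---|---|
| Power | 78.0% | 81.5% | 84.5% | 87.0% | 89.2% | 90.1% | 91.0% |

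The first N above 90% is 39; with equal sequences it is 40.

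**Step 6, the amendment.** The head count itself adds up: 31 − 17 = 14 viable, plus 18 of the 21 new participants (21 × 0.85 = 17.85), gives 32. The power attached to that 32 does not follow. Even with no further dropout, 52 − 17 = 35 evaluable participants would give about 86%.

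**Step 7, precision.** The expected half-width of the 90% CI on the log scale at N = 32 is 1.697 × 0.0734 = 0.1246. The interval is therefore about GMR × exp(−0.1246) to GMR × exp(0.1246), that is GMR × 0.88 to GMR × 1.13.

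**The case against.** The arithmetic is not in dispute; the case on the other side concerns how much it matters.

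- **No formal test.** Protocol 9.1 and SAP 4.1 say that no hypothesis test decides success, that the bounds are a very conservative standard, and that an effect outside them does not mean a failed study. The mixed model, the GMR and the 90% CI do not use the power figure. This stands and limits the consequence. It does not make the number right: the power statement is the plan's only quantified support for adequate precision, and Protocol 9.2 still uses the bounds to judge whether there is inhibition.
- **Little precision is lost.** The expected CI factors are 0.883 to 1.133 at 32 completers and 0.895 to 1.117 at 40. This stands, and is why no larger sample is requested.
- **32 is a conventional size.** It is the smallest even N with at least 80% power, so calling it sufficient can be defended. But the amendment ties sufficiency to the power described just before it, which is 90%.
- **32 is a floor.** The 17 participants' samples are still under stability investigation. If some prove usable, power rises (89.2% at 38, 91.0% at 40). This stands for the power eventually achieved, but not for the claim about 32.
- **The single-test explanation is an inference.** This stands. The error does not depend on it.

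**Conclusion.** The stated power is wrong as written in Protocol 9.2 and SAP 4.2. Under the plan's inputs, 32 completers give 81.5% power per PK parameter against the stated 90%, and a type II error of 18.5% against 10%. No reading consistent with two one-sided 5% tests and a CV of 0.30 reaches 90%. The amended total of about 52 rests on the same figure.

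The result assumes exactly 32 evaluable participants split evenly, a CV of 0.30 and a true ratio of 1. Two conditional figures show the direction if those conditions are less kind, but the finding does not rest on them:

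- At a true ratio of 1.05, power is 72.7%.
- If Cmax and AUC∞ both had to lie within the bounds, joint power would be about 69% at an assumed correlation of 0.5 and about 76% at 0.9. Neither document sets such a rule or gives a correlation.

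The treatment estimate and its interval are unaffected.

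**What to change.** In Protocol 9.2 and SAP 4.2:

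1. Replace the 90% claim with approximately 82% power per PK parameter for 32 completers, under the stated assumptions.
2. Add the expected precision at 32 completers: a 90% CI of about GMR × 0.88 to GMR × 1.13. This is the quantity that Protocol 9.1 says the size was meant to secure.
3. State that 90% power would need 40 completers with balanced sequences.
4. In the amendment paragraph of Protocol 9.2, let the reference back to sufficient power point to the corrected figure.

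The cost is wording in two sections, and the stated power becomes less favourable. No change to the design, analysis or enrolment is requested. For information only, holding to 90% would have meant 40/0.85, rounded up to 48 randomized, instead of 38. On the amendment's logic it would mean 40 − 14 = 26 more completers, 26/0.85 rounded up to 31 more randomized, and about 31 + 31 = 62 in total instead of 52.

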- Treatment B: One 150 mg bupropion HCl salt tablet (WELLBUTRIN SR 150) + 4 × 15 mg ALXN1840 EC tablets with 240 mL water (fasting).

Participants will receive each treatment as a single dose administration in the sequence as defined below.

Sequence number	Treatment sequence		Total
	Study Period 1	Study Period 2	
1	A	В	26
2	В	A	26
Total			52

Treatment A -One 150 mg bupropion HCl salt tablet (WELLBUTRIN SR 150) with 240 mL water (fasting) Treatment B – One 150 mg bupropion HCl salt tablet (WELLBUTRIN SR 150) + 4 × 15 mg ALXN1840 enteric-coated tablets with 240 mL water (fasting)

The time between dosing bupropion alone or in combination with ALXN1840 in each treatment sequence will be a minimum of 14 days. Based on the estimated mean ALXN1840 half-life of approximately 2 days in healthy participants (under oral dose of 60 mg), a 14-day period between doses of bupropion is considered sufficient to eliminate, on average, approximately more than 99.2% of the plasma total Mo before the next dose of bupropion is administered. The mean elimination half-life (±SD) of bupropion after chronic dosing is 21 (± 9) hours (WELLBUTRIN SR). A 14-day period between doses of bupropion is sufficient to eliminate, on average, more than 99.2% of the plasma bupropion before the next dose of bupropion is administered.

Participants will return to the CRU on Day 15 (\pm 2 days) following Period 2 dosing for the EOS Visit with follow-up procedures, and to determine if any adverse events (AEs) have occurred since the last study visit. If participants withdraw from the study early, they will be seen and assessed by the Principal Investigator, and whenever possible, they are to undergo the procedures associated with the EOS Visit. Participants may be replaced at the discretion of Alexion.

[figure not shown]
Participants may be asked or required to stay in the CRU between Periods 1 and 2, and/or before the EOS visit, for their own safety, and also to maintain the integrity of the conduct of the study.

Data Monitoring Committee:

There will not be a Data Monitoring Committee, but provision is included for an ad hoc Safety Review Committee, if needed.

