The End of Study (EOS) Visit will occur approximately 4 days after discharge from Period 2 after collection of the nominal 336-hour PK sample.

This study will include approximately 52 participants to complete at least 32 participants.

Participants will be randomized to one of two sequences as described in Table 3.

Table 3: Study Design

Sequence number	Treat	Total	
	Study Period 1	Study Period 2	
1	A	В	26
2	В	A	26
Total			52

Treatment A - One 150 mg bupropion HCl salt tablet (WELLBUTRIN SR 150) with 240 mL water (fasting) Treatment B - One 150 mg bupropion HCl salt tablet (WELLBUTRIN SR 150) $+ 4 \times 15$ mg ALXN1840 enteric-coated tablets with 240 mL water (fasting)

At the Investigator's discretion, additional participants may be screened to allow for a full enrollment of the study; therefore, it is possible that all eligible participants may not be included. Participants not included in the study will be discharged without dosing on Day 1.

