4.4. End of Study Definition

A participant is considered to have completed the study if he/she has completed all phases of the study including the last scheduled procedure shown in the Schedule of Activities (SoA).

The end of the study is defined as the date the last participant completes the last visit as shown in the SoA (Table 1).

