AE	adverse event
AUC	area under the plasma concentration versus time curve
	area under the plasma concentration versus time curve from time 0 to
AUCt	the last quantifiable concentration
	area under the plasma concentration versus time curve from zero to
AUC_∞	infinity
AUEC	area under the effect versus time curve
ALIEC	area under the effect versus time curve from time 0 to last quantifiable
AUECt	concentration time
BLQ	below the limit of quantification
BMI	body mass index
CI	confidence interval
CL/F	apparent oral clearance
C _{max}	maximum observed plasma concentration
CRF	case report form
CRU	clinical research unit
CTCAE	Common Terminology Criteria for Adverse Events
CV	coefficient of variation
EC	enteric-coated
ECG	electrocardiogram
eDISH	evaluation of drug-induced serious hepatotoxicity
E _{max}	maximum observed PD concentration in plasma
EOS	End of Study
ET	early termination
FSH	Follicle stimulating hormone
GMR	geometric mean ratio
ICF	informed consent form
IQR	interquartile range
MedDRA	Medical Dictionary for Drug Regulatory Activities
MSE	mean-square error
PBC	primary biliary cholangitis
PD	pharmacodynamic
РК	pharmacokinetic(s)
QTcF	QT interval corrected for heart rate using Fridericia's formula
Q1	quartile 1
Q3	quartile 3
RBC	red blood cell
SAE	serious adverse event
SAP	statistical analysis plan
SD	standard deviation

Abbreviation	Term
TEAE	treatment-emergent adverse event
TESAE	treatment-emergent serious adverse event
TE _{max}	time to reach maximum observed pharmacodynamic concentration in plasma
T _{lag}	time delay between the time of dosing and time of appearance of drug concentration in plasma
T _{max}	time to reach maximum observed concentration in plasma
t _{1/2}	terminal elimination half-life
V _d /F	apparent volume of distribution
WD	Wilson disease
% AUC _{extrap}	AUC extrapolated from time t to infinity as a percentage of total AUC $_{\infty}$
λ_z	apparent terminal-phase elimination rate constant

1. Introduction

This document outlines the statistical methods to be implemented during the analysis of data collected within the scope of Alexion Pharmaceuticals, Inc., protocol ALXN1840-HV-103 (A Phase 1, Randomized, 2-Period, 2-Sequence, Cross-over Study to Determine the Effect of ALXN1840 on the Metabolism of a CYP2B6 Substrate in Healthy Participants.), original version, dated 28 Apr 2020. The purpose of this statistical analysis plan is to define the planned statistical analysis of the study data consistent with the study objectives.

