4.4.2. Pharmacokinetic/Pharmacodynamic Analysis Set

The PK analysis set will include all participants who have sufficient plasma samples to have evaluable PK data for bupropion and/or total molybdenum (as a measure of ALXN1840) in plasma.

The Pharmacodynamic (PD) analysis set will include all participants who have sufficient plasma samples to have evaluable PD data for total copper or PUF copper.

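### Does the amended total of 52 fall short of 32 completers, given that 21 × 0.85 is 17.85 and the other 14 participants carry no dropout allowance?

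*Protocol*

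**What the plan says.** Protocol 9.2 sets the requirement at 32 completed participants and obtains the original 38 by allowing for 15% dropout. It then reports that, of 31 randomized by the date of the amendment, 17 "were anticipated to not have viable PK samples (pending further bioanalytical stability investigation"), and that "an additional 21 participants will be randomized to complete at least 18 of the 21 (assuming a similar 15% dropout rate" applies to the new group. The total becomes about 52. The dropout allowance is tied to one group only: "assuming a similar 15% dropout rate for the additionally enrolled participants".

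Protocol 4.1 repeats the target: "This study will include approximately 52 participants to complete at least 32 participants". The Synopsis adds a safeguard: "Participants may be replaced at the discretion of Alexion". Completion is defined by study procedures in Protocol 4.4: "A participant is considered to have completed the study if he/she has completed all phases of the study". SAP 4.4.2 defines its PK set by "evaluable PK data for bupropion and/or total molybdenum".

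Protocol 9.1 states that no formal null hypothesis decides success or failure. The 80% to 125% limits were used to size the study for precision.

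**The concern.** The calculation appears to leave no slack. The 14 participants outside the affected 17 enter the count in full, and 9.2 does not say how many of them had finished both periods when the amendment was written. The amendment summary and section 4.1 do not say either. The 21 added participants are expected to give 17.85 completers at 15% dropout, so a figure worded as a minimum is really about the average. The original plan rounded its requirement up (37.65 to 38), whereas the amendment rounded down (21.18 to 21).

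The wording of the target adds to the doubt. Completion is defined by visits and procedures, and the SAP's PK set admits participants with molybdenum data alone. The primary comparison needs bupropion PK, ideally from both periods. If the study ended with clearly fewer than 32 such participants, the interval for the geometric mean ratio would be wider than planned. The amendment's only substantial revision is this number, so it is fair to ask whether it holds.

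**Working it through.** **Inputs, all from Protocol 9.2.** 32 completers required; 15% dropout; 31 randomized; 17 anticipated lost; 21 added; intra-participant CV 0.30; true ratio 1; limits 0.80 to 1.25; 5% for each one-sided test.

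**The plan's own figures**
- Original: 32 / 0.85 = 37.65, rounded up to 38.
- Not among the 17: 31 − 17 = 14. Still needed: 32 − 14 = 18.
- Added: 18 / 0.85 = 21.18, which is 21 to the nearest whole number and 22 rounded up.
- In reverse: 21 × 0.85 = 17.85, which rounds to 18. Eighteen of 21 corresponds to 3/21 = 14.3% dropout.
- Total: 31 + 21 = 52. Rounding up would give 53.

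The stated figures therefore reproduce, with a rounding difference of one participant.

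**Chance of reaching 32** (binomial, each at-risk participant completing with probability 0.85; none of the 17 recovered, nobody replaced)

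| Assumed status of the 14 | Expected total | Chance of at least 32 |
|---|---|---|
| All completed | 14 + 17.85 = 31.85 | P(≥18 of 21) = 61% |
| 7 completed, 7 at risk | 7 + 0.85 × 28 = 30.80 | P(≥25 of 28) = 38% |
| All at risk | 0.85 × 35 = 29.75 | P(≥32 of 35) = 21% |
| Original plan, 38 at risk | 0.85 × 38 = 32.30 | P(≥32 of 38) = 66% |

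Adding 22 instead of 21, with the 14 complete, gives P(≥18 of 22) = 77%.

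Recovery works in the other direction. Suppose 2 of the 17 prove viable. If those 2 and the 14 have all completed, only 16 of the 21 are needed, with a chance of 92%. If all 37 are still at risk, the chance is 51%.

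Only the original-plan row rests wholly on figures in the documents. The status of the 14 and the number recovered are assumptions chosen to show the range.

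**Effect on precision.** The log-scale within-participant SD is √ln(1 + 0.30²) = 0.2936. The standard error of the treatment difference is 0.2936 × √(2/n), on n − 2 degrees of freedom.
- n = 32: SE 0.0734, t = 1.697, 90% CI around a ratio of 1 is 0.883 to 1.133.
- n = 30: SE 0.0758, t = 1.701, 90% CI is 0.879 to 1.138.

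**Effect on power.** Exact power of the two one-sided tests is 81.5% at 32 and 78.0% at 30. Averaged over the binomial number of completers, it is 81.7% for the original 38, 81.1% for 14 fixed plus 21 at risk, and 77.2% for all 35 at risk. With the 14 complete, the amendment therefore costs 81.7 − 81.1 = 0.6 points against the original plan. The gap between these figures and the 90% stated in 9.2 is a separate matter that does not come from the dropout arithmetic.

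**The wording of the target.** The sentence that sets the aim of 32 follows directly from the explanation that the 17 are discounted because their samples may not be viable. In context, then, it cannot be counting them. The model in Protocol 9.4.3.1 and SAP 9.5 is fitted to log bupropion Cmax, AUCt and AUC∞. A participant with molybdenum data only has no value to enter and contributes nothing to the primary estimate.

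**The case for a change.** The best argument for a change is that 9.2 presents 32 as the number needed for sufficient power, yet a reader cannot tell from it whether reaching 32 is somewhat better than even or unlikely. With 21 added and every one of the 14 needed, losing just one of the 14 lowers the chance from 61% to 37%. Enrolment stood at 31 of 38 when the amendment was written, so some of the 14 may still have been in the study. One sentence giving their status would settle it, at no cost in participants, visits or samples.

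Part of this stands: the status of the 14 is not given, and describing 18 as a minimum overstates what 15% dropout delivers. It does not establish a shortfall. Applying dropout only to the new group is what one would do if losses among the first 31 were already known, although the text does not say so. The 21% case needs three unfavourable conditions together: all 14 at full risk, no recovery from the 17, and no replacement. The protocol treats the loss of the 17 as provisional and allows replacement.

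The SAP still refers to the protocol's "original version, dated 28 Apr 2020" and to 38 participants. That is a version-alignment matter with no bearing on whether 52 is enough.

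**Conclusion.** No change follows. The difference between 17.85 and 18 is rounding: 21 or 22 added, 52 or 53 in total, within a number the protocol gives as approximate and a target it calls an aim. The original 38 carried nearly the same risk of missing 32 (66% chance of success against 61%), so the amendment brings in no new weakness on this count, provided the 14 had completed.

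The unstated status of the 14 is a gap in the description. At its least favourable it puts the expected number at 29.75. With 30 participants each confidence limit moves by 0.004 to 0.005, and average power falls by 81.5 − 77.2 = 4.3 points from its value at 32, in a study with no formal success criterion. The sponsor can presumably resolve the question from site records, and the discretion to replace participants covers a real shortfall. Neither the definition of completion nor the breadth of the SAP's PK set alters which data enter the bupropion model.

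This rests on the protocol's CV of 0.30, a true ratio of 1, independent dropout at 15%, and the assumed range for the 14. It takes the target of 32 as given and does not judge whether 32 supports the stated 90% power.
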